### **9.3.8. Other assessments**

#### **Immunoscore and PD-L1 analyses and MGMT Status Assessment**

A local pathology report will constitute adequate documentation of histology for study inclusion; however, the tumor block used for diagnosis of GBM must be collected for each patient and sent for biomarker analyses, immunoscore determination and MGMT assessment (if not already done). The availability of these samples is mandatory for participation into the study, and they must be sent within 2 months after patient's entering the study.

Paraffin embedded blocks containing formalin-fixed tumor tissue representative of the glioblastoma diagnosis is the preferred sample if available, and of sufficient quality), otherwise, a partial tumor block, or pathology material should be sent If surgery was not performed but biopsy was performed (or if it is not possible to send FFPE tumor tissue blocks) **at least 10 unstained, uncovered slides** must be sent.

#### **Neurocognitive Function**

Baseline neurocognitive function has been shown to have prognostic value in patients with GBM. The P300 evoked potential is an electrophysiological measure of a person's capacity to assign attention to a specific stimulus. The measure has shown good correlation (ICC of 0.7) with cognitive status in neurodegenerative diseases. It is a painless, easy measure to obtain. We hope that it will circumvent some of the shortcomings of using neuropsychological scales in assessing the overall general neurocognitive status of patients.

The P300 will be performed at baseline, every 52 weeks and at end of study visit (week 260 or at PD)

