### **Electrophysiological assessment**

A P300 evoked potential will be obtained at baseline and every 52 weeks /or end of study visit (depending whether the end of study occurs prior or after the week 260 visit) for all patients. The P300 will be done in lieu of cognitive assessment. The baseline value and its change will be correlated with clinical outcomes.

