### **Exploratory:**

The correlation between OS and PFS and the prevalence of PD-L1 expression on tumor cells and microglia/macrophages within the tumor, the histological immunoscore.

The correlation between OS and PFS in relation to the baseline corticosteroid dose, the total cumulative corticosteroid dose over the whole study duration, the total cumulative temozolomide dose per BSA since diagnosis, the baseline value and the change from baseline to week 52 and every 52 weeks /or the end of study visit neurocognitive function as measured by the evoked potential P300 and the incidence and severity of irAE's.

The change between baseline biomarker results and those obtained from biomarkers in tissue samples from patients with second surgical resection i.e., treatment failures

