### **5.3. Exploratory**

The correlation between OS and PFS and the prevalence of PD-L1 expression on tumor cells and microglia/macrophages within the tumor, the histological immunoscore.

The correlation between OS and PFS and the baseline corticosteroid dose, the total cumulative corticosteroid dose over the whole study duration, the total cumulative dose of temozolomide since diagnosis, the baseline value and the change from baseline to week 52 visit and/or the end of study neurocognitive function as measured by the evoked potential P300 and the incidence and severity of irAE's.

The change between baseline biomarker results and those obtained from biomarkers in tissue samples from patients with second surgical resection i.e. treatment failures

The description of the time period in which radiological progression was seen in clinically stable patients whose imaging was subsequently followed by radiological stabilization or regression

The description of the time period in clinically stable patients before radiological evidence tumor regression occurred

The change in P300 evoked potential values and its correlation with clinical outcomes

**Safety monitoring:** There will be an internal DSMB which will make annual reviews.

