#### 12.3.3. Exploratory

The incidence of PD-L1 expression on tumor cells and microglia/macrophages within the tumor will be determined and correlated to OS and PFS and other iRANO endpoints

The histological immunoscore will be determined and tested for association with OS, PFS, and other iRANO endpoints using logistic regression.

The association between 12 months OS and PFS with baseline neurocognitive function as measured by the evoked potential P300 (normal), the baseline corticosteroid dose, the average daily corticosteroid dose over the whole study duration, the extent to which patients complete the full 6 cycles of temozolomide based on temozolomide toxicity and the incidence and severity of treatment related irAE's will be tested using logistic regression.

The change if any in histological markers on tissue obtained from repeat resection

The estimation of the time period in which radiological progression was seen in clinically stable patients whose imaging was subsequently followed by radiological stabilization or regression

The estimation of the time period in clinically stable patients before radiological evidence of tumor regression occurred

The change in P300 will be determined and correlated with clinical outcomes as per iRANO.

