1.3.3. Exploratory

The incidence of PD-L1 expression on tumor cells and microglia/macrophages within the tumor will be determined and correlated to OS and PFS and other iRANO endpoints

The histological immunoscore will be determined and tested for association with OS, PFS, and other iRANO endpoints using logistic regression.

The association between 12 months OS and PFS with baseline neurocognitive function as measured by the evoked potential P300 (normal), the baseline corticosteroid dose, the average daily corticosteroid dose over the whole study duration, the extent to which patients complete the full 6 cycles of temozolomide based on temozolomide toxicity and the incidence and severity of treatment related irAE's will be tested using logistic regression.

The change if any in histological markers on tissue obtained from repeat resection

The estimation of the time period in which radiological progression was seen in clinically stable patients whose imaging was subsequently followed by radiological stabilization or regression

The estimation of the time period in clinically stable patients before radiological evidence of tumor regression occurred

The change in P300 will be determined and correlated with clinical outcomes as per iRAN

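### Change in P300 is correlated with OS, PFS and iRANO outcome although progression can set the date of the follow-up P300, so an association could come from timing or from progression itself

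*Protocol*

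**What the plan says.** **When P300 is measured.** Protocol 9.3.8 (Neurocognitive Function): "The P300 will be performed at baseline, every 52 weeks and at end of study visit (week 260 or at PD". The synopsis (Electrophysiological assessment) words it differently: "A P300 evoked potential will be obtained at baseline and every 52 weeks /or end of study visit". Table 1 marks P300 at baseline, week 52 and the end visit only.

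**When the end visit occurs.** Section 9.3.4 ties an end visit on iRANO progression to patients who do not wish to continue treatment. The synopsis and section 4.2 allow avelumab to continue after confirmed progression, with renewed consent.

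**What is done with the change.** The synopsis plans to correlate OS and PFS with "the baseline value and the change from baseline to week 52 and every 52 weeks /or the end of study visit". Section 5.3 has "the change from baseline to week 52 visit and/or the end of study neurocognitive function as measured by the evoked potential P300". Section 12.3.3 adds: "The change in P300 will be determined and correlated with clinical outcomes as per iRANO"; SAP 1.3.3 repeats this line. The exploratory objectives (synopsis and section 3.3) and the synopsis's tertiary endpoints carry the same plan.

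**What is done with the baseline value.** The logistic regression in SAP 1.3.3 and protocol 12.3.3 is limited to baseline P300: "The association between 12 months OS and PFS with baseline neurocognitive function as measured by the evoked potential P300 (normal".

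Neither document says which visit supplies the change, and neither gives a landmark, a time-dependent analysis or an adjustment for elapsed time.

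**The concern.** The date of the follow-up P300, and the disease state in which it is taken, can depend on the outcome with which the change is correlated. This opens two separate routes to an association that carries no prognostic information.

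- **Unequal elapsed time.** A patient who progresses and stops at week 20 contributes a 20-week change; a patient who reaches week 52 contributes a 52-week change. If P300 drifts over time in everyone, the size of the change tracks time on study, and so PFS.
- **Progression itself.** Clinical progression is defined in section 5.2 as sustained neurological deterioration. A P300 taken then may register the event rather than precede it.

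The synopsis uses P300 in place of cognitive assessment, and its change is a stated exploratory objective. What is at stake is whether any reported association could be interpreted.

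**Working it through.** **Plan figures reproduced.** The plan states no power or precision for the P300 analysis. Its general precision for a mean is 1.96/√30 = 0.358 SD, which agrees with the stated 0.36 SD. The one-year rates used below, 60% OS and 27% PFS, are those in SAP 1.3.2. They reproduce its cut-offs: with n = 30, the exact one-sided probability of at least 21 survivors at 60% is 0.176, and of at least 11 progression-free at 27% is 0.161, both below 0.2.

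**Patients in each group if avelumab has no effect.**
- Progression-free at week 52: 30 × 0.27 = 8.1.
- Progressed or dead before week 52: 30 × 0.73 = 21.9.
- Alive at week 52: 30 × 0.60 = 18.

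**Difference in elapsed time.** Assume exponential PFS. The weekly hazard is λ = −ln(0.27)/52 = 0.0252, so 1/λ = 39.7 weeks. The mean event time among those with an event before week 52 is 1/λ − 52 × 0.27/0.73 = 39.7 − 19.2 = 20.5 weeks. Early progressors measured at PD would thus be seen at about week 20 on average, the others at week 52.

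**Simulation** (4,000 trials per scenario, n = 30). The following are assumptions, not in the documents: exponential and fully observed PFS, a value for all 30 patients, SD of P300 change = 1, and no predictive value. The model is

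change = drift × (weeks elapsed/52) + PD effect × (progressed before week 52) + N(0,1).

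Entries are the share of trials with two-sided p < 0.05: Spearman correlation of change with PFS / t-test of early progressors against the rest.

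| Assumed | Measured at PD or week 52 | All measured at week 52 |
|---|---|---|
| Neither drift nor PD effect | 5% / 5% | about 5% / 5% |
| Drift 0.5 SD per year | 14% / 10% | about 5% / 5% |
| Drift 1 SD per year | 40–43% / 27% | about 5% / 5% |
| PD effect 0.5 SD | 14% / 22% | same |
| PD effect 1 SD | 37% / 63% | same |

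The range in the third row is the spread between repeat runs. In the last two rows the columns agree by construction: without drift, the measurement date does not enter the formula once the PD effect persists. Only the drift rows isolate the schedule.

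**Direction.** A drift and a PD effect of 1 SD each nearly cancel on the rank test when they act in the same direction (6% / 14%) and reinforce each other when they act in opposite directions (90% / 94%).

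**Treatment past progression.** If half of the early progressors continue and are measured at week 52, a 1 SD drift falls to 13% / 9%, while a persisting 1 SD PD effect stays at 37% / 63%.

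**Landmark check.** Taking P300 change at one early time (week 12, for illustration only) in patients still progression-free, and relating it to later PFS, gives 4.4% to 5.7% in every scenario.

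**The case against.** The strongest reply is that the plan asks only for correlation, in a study whose analysis is to be mainly descriptive. The wish to predict treatment response is attached to the immunoscore and PD-L1, not to change in P300. If P300 does worsen at progression, a correlation is genuine tracking. No test or significance level is set for the change analysis. This largely stands against calling the PD-effect results false positives. It does not answer the drift results, where P300 neither predicts nor tracks disease and the association comes only from the dates of measurement.

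A reader might infer that every patient who progresses is measured at progression. The documents do not support that:
- Patients may be treated past PD, and section 9.3.4 then requires no end visit at PD.
- End visits also follow toxicity or patient choice.
- Radiological progression before 6 months needs confirmation 3 months later and is backdated (section 5.2), so an end visit at confirmation falls after the PD date.
- Patients who progress after week 52 also have a week-52 value.
- Patients who die before an end visit may have no follow-up value. About 12 of 30 deaths by week 52 are expected at 60% OS (30 × 0.40), while the simulation gives everyone a value.

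These points weaken the link between outcome and date without removing it. They also show that sections 9.3.8 and 9.3.4 do not agree on when the end-visit P300 is taken.

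**Conclusion.** The point holds in a limited form. Progression can set the date of the follow-up P300, the change is correlated with outcomes counted from baseline, and nothing in the plan separates prediction from elapsed time or from the event itself. An association found this way could not be read as P300 change predicting outcome.

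Two stronger readings go too far. One is that the change must correlate with outcome: with neither drift nor PD-related worsening the rate is the nominal 5%, and the two effects can cancel. The other is that the 22% and 63% t-test rates measure the fault in the schedule: they are the same when everyone is measured at week 52. The part due to the schedule is the rise from about 5% to about 14% or 40% under a drift of 0.5 or 1 SD per year. Those drifts are assumptions; the documents give no figure for P300 change over time, so the real size and direction are unknown.

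Only an exploratory objective is affected. The primary safety endpoint, the OS/PFS decision rule and the baseline-P300 regression are untouched.

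**What to change.** Amend SAP 1.3.3 and carry the same wording to every place in the protocol that plans the change correlation: the synopsis (objectives, exploratory and tertiary endpoints) and sections 3.3, 5.3 and 12.3.3.

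1. Use baseline P300 as the only P300 predictor of OS and PFS counted from baseline.
2. Relate change to week 52 only to later outcomes: OS after week 52 in patients alive at week 52 (up to about 18 of 30 at the plan's 60% rate), and PFS after week 52 in patients alive and progression-free at week 52 (about 8 of 30 at the 27% rate). Only patients with a week-52 P300 can contribute.
3. Report end-visit and PD-time P300 descriptively, with time since baseline and the reason for the visit, and keep these values out of the correlations.
4. Reconcile sections 9.3.8 and 9.3.4 on when the end-visit P300 is taken, including for patients treated past progression.

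The cost is wording; no test is added. The protocol edits must go to the ethics board under section 15.2. The drawback is that the landmark analyses are small and can support only description.

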**Table 1: STUDY ACTIVITIES**

Tests and Evaluations	Screening Visit	Combination/ phase Week 0 to 24 Visit window: $\pm 2$ days														Monotherapy phase Week 26 to 52  Visit window: $\pm 2$ days														Extended safety follow-up phase 
		0	2	4	6	8	10	12	14	16	18	20	22	24	26	28	30	32	34	36	38	40	42	44	46	48	50	52		
Week	-12 to -1	0													26	28	30	32	34	36	38	40	42	44	46	48	50	52	EOS	
Informed Consent	X																													
Demographics Medical History	X																													
Physical Exam	X	X		X		X		X							X					X					X			X	X	
Neurological Exam	X	X		X		X		X							X					X					X			X	X	
Karnofsky	X	X																												
Vital Sign	X	X	X	X	X	X	X	X	X	X	X	X	X	X	X	X	X	X	X	X	X	X	X	X	X	X	X			
Lab's 	X	X	X	X	X	X	X	X	X	X	X	X	X	X	X	X	X	X	X	X	X	X	X	X	X	X	X			
ECOG	X	X	X	X	X	X	X	X	X	X	X	X	X	X	X	X	X	X	X	X	X	X	X	X	X	X	X			
MRI or CT scan		X																											X	X
P300		X																											X	X
AE's and concomitant medications		X	X	X	X	X	X	X	X	X	X	X	X	X	X	X	X	X	X	X	X	X	X	X	X	X	X	X		
Pre-infusion questionnaire		X	X	X	X	X	X	X	X	X	X	X	X	X	X	X	X	X	X	X	X	X	X	X	X	X	X			
Avelumab infusion Q 2 weeks		X	X	X	X	X	X	X	X	X	X	X	X	X	X	X	X	X	X	X	X	X	X	X	X	X	X			
Temozolamide		X		X		X		X		X		X		X		X		X		X		X		X		X				

See foot note on the next page

- 1 The Extended Safety phase will involve a site visit at day 30 and telephone follow-up at day 60 and 90 post end of treatment. A second site visit may be required if there is any concern
2. Patients who withdraw prematurely from the treatment or complete the 260 weeks of treatment will be offered to enter the Extended safety follow-up phase
3. Lab's: **Hematology** will include Hemoglobin, platelet count, WBC count, absolute neutrophils, and lymphocytes. **Coagulation** will include INR, and aPTT (at screening or baseline only). **Blood chemistry** will include total bilirubin, AST, ALT, LDH, alkaline phosphatase, serum albumin, phosphate, serum creatinine, and electrolytes (sodium, potassium, calcium), glucose, amylase, lipase, TSH, GGT, CK. **Urinalysis** will include urine dipstick test. **Serum  $\beta$ -HCG** must be performed at screening in women of childbearing potential. Subsequent **urine  $\beta$ -HCG** must be collected monthly. Additional tests may be done at the discretion of the investigator for patient safety.
- TSH T4 will be collected Q8weeks and repeated at the Extended Safety visit
4. study visit will continue Q2weeks until the occurrence of a termination event.

Survival telephone visits will be performed every 4 weeks until death or the end of the study, whichever occurs first

## **10. INVESTIGATIONAL MEDICINAL PRODUCT**

### **10.1. Dose and Schedule of Test Drug**

Avelumab is a fully human IgG1 antibody directed against PD-L1. Avelumab binds PD-L1 and blocks the interaction between PD-L1 and its receptors PD-1 and B7.1. This removes the suppressive effects of PD-L1 on anti-tumor CD8+ T cells, resulting in the restoration of cytotoxic T cell response.

Avelumab will be administered intravenously every 14 days starting the same day as the first day of the first 5 days po temozolomide treatment. Temozolomide's 28 days cycle will be repeated 6 times or until grade 3 or higher temozolomide related treatment AE's. Avelumab will be continued IV q14 days for 260 weeks or until grade 3 or higher avelumab treatment-related AE's occurs and independent of whether the patient continues or completes the 6 cycles of temozolomide.

Avelumab may be withheld temporarily in the case of irAE according to the irAE's algorythms (table 3)

Temozolomide dose may be adjusted or withheld according to the directives in the temozolomide's product monograph (appendix 4)

### **10.2. Avelumab**

Avelumab drug product is a sterile, clear, and colorless concentrate for solution presented at concentration of 20 mg/mL in European Pharmacopeia (Ph. Eur.) and United States Pharmacopeia (USP) type I glass vials closed with a rubber stopper and sealed with an aluminum Flip Off® crimp seal closure.

Each single-use vial contains 200 mg of avelumab as a preservative-free acetate-buffered solution (pH 5.2) containing Mannitol, and Polysorbate 20 (Tween-20). For avelumab drug product, only excipients that conform to the current Ph. Eur. and/or the current USP are used.

#### **Instructions for Avelumab Administration and Storage**

Avelumab drug product must be stored at 2°C to 8°C until use. The storage condition is based on data from ongoing long term stability studies with avelumab. Avelumab drug product stored at room (23°C to 27°C) or higher temperatures for extended periods of time might be subject to degradation. Avelumab drug product must not be frozen. Rough shaking of the solution must be avoided.

For administration in clinical trials, avelumab drug product must be diluted with 0.9% saline solution (sodium chloride injection) supplied in an infusion bag; alternatively, a 0.45% saline solution can be used if needed. The chemical and physical in-use stability for the infusion solution of avelumab in 0.45% or 0.9% saline solution has been demonstrated for a total of 24 hours at room temperature. However, from a microbiological point of view, the diluted solution should be used immediately and is not intended to be stored unless dilution has taken place in controlled and validated aseptic conditions. If not used immediately, in-use storage times and conditions prior to administration are the responsibility of the user.

**No other drugs should be added to the solution for infusion containing avelumab.**

Detailed information on infusion bags and medical devices to be used for the preparation of the dilutions and subsequent administration will be provided in the manual of preparation.

To prepare the dilutions, subsequent preparation steps must be accomplished by adequate trained personnel:

Prior to the preparation of the dilution for final infusion, allow each vial to equilibrate to room temperature. Use a disposable syringe equipped with a needle of suitable size to remove a volume of sodium chloride solution to be replaced by avelumab from the infusion bag and discard the removed solution. Use a new disposable syringe equipped with a needle of suitable size to inject a volume of avelumab drug product identical to the discarded volume of sodium chloride solution into the infusion bag. Gently invert the mixture 10 times. Infusion bags must not be shaken, in order to avoid foaming or excessive shearing of the protein solution. The preparation must be carefully inspected as it should result in a homogeneous looking clear solution, free of visible particles. For detailed information on the assigned dose levels and the concrete volumes to be replaced to prepare the target doses, please refer to the clinical trial protocol or to the manual of preparation.

### **10.3. Temozolomide**

Institutions should follow their standard guidelines for temozolomide. Temozolomide is taken orally on a daily basis during the chemoradiotherapy (75 mg/m^2 p.o.) and for the first 5 days of each cycle during the six cycles of the Combination Phase with a starting dose of 150 mg/m^2 po qd which in the absence of tolerability or toxicity issues may be escalated to 200mg/m^2 po qd in the second or subsequent cycles.

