### **4.2. Treatment Phases of the Study**

**Combination Phase:** Upon completion of the standard combination therapy of radiotherapy (total dose 60 Gy, administered as daily 2Gy fractions, 5 days/week or as per local standard) and temozolomide (75 mg/m^2/day p.o. qd) and a treatment break of no more than 21 days, the combination phase will start. Patients will receive temozolomide and avelumab for 6 cycles of 28 days each. During the 1st cycle Temozolomide will be given the first 5 days at a dose of 150mg/m^2/day p.o. In the next cycle, the temozolomide dose should be escalated to 200/mg/m^2 if permitted by the patient's hematological and non-hematological toxicity profile (as per NCI-CTC AE version 5). The temozolomide dose will be adjusted according to hematological and non-hematological toxicity as per temozolomide's product monograph (appendix 4). Avelumab will be administered on day 1 and day 15 of each cycle at a dose of 10mg/kg IV. Avelumab therapy will be withheld according to the occurrence and severity of avelumab emergent adverse events as per table 3. Patients will continue the

combination of temozolomide (150 – 200mg/m^2 per day PO X5 days Q28days) and avelumab (at 10mg/kg dose, IV on days 1 and 15 per cycle) until 6 cycles are completed or until the occurrence of a termination event.

**Monotherapy Phase:** Upon completion of the Combination Phase or upon stopping temozolomide because of temozolomide related toxicity/tolerability issues or patient choice, the patient will continue into the avelumab Monotherapy Phase. Avelumab 10mg/kg IV Q2weeks will be continued as monotherapy until the occurrence of a termination event defined as one of the following: 1) clinical evidence of neurological deterioration resulting in an ECOG score of at least 3 or more, unexplained by other comorbidities, unchanged by an increase in corticosteroid dose and sustained for at least two weeks or 2) treatment emergent adverse event (TEAE) of grade 3 or more or 3) withdrawal of patient consent.

Patients who experience irAE's may according to table 3 directives have their avelumab therapy suspended.

The use of Bevacizumab or re-irradiation will not be allowed in the study and will be considered as evidence of a termination event.

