## **11. SAFETY ASSESSMENT**

### **11.1. Adverse Event (AE) and AE Reporting**

#### **11.1.1. Definition of a Clinical Adverse Events**

Per the International Conference of Harmonization (ICH) an AE is any unfavorable and unintended medical occurrence/sign (including an abnormal laboratory finding), symptom or disease in a patient or clinical investigation subject administered a pharmaceutical product and which does not necessarily have a causal relationship with this treatment.

An AE can therefore be any unfavorable and unintended sign, symptom, or disease temporally associated with the use of a medicinal product, whether or not considered related to the medicinal product. Pre-existing conditions which worsen during a study are also to be reported as AEs.

Each AE term is mapped to a MedDRA preferred term.

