##### **Maintenance Phase**

Four weeks after completing the TEMODAL® + RT (Radiotherapy) phase, TEMODAL® is administered for an additional 6 cycles of maintenance treatment. Dosage in Cycle 1 (maintenance) is 150 mg/m^2 once daily for 5 days followed by 23 days without treatment. At the start of Cycle 2, the dose is escalated to 200 mg/m^2, if the CTC non-hematologic toxicity for Cycle 1 is Grade  $\leq 2$  (except for alopecia, nausea and vomiting), absolute neutrophil count (ANC) is  $\geq 1.5 \times 10^9/L$ , and the platelet count is  $\geq 100 \times 10^9/L$ . If the dose was not escalated at Cycle 2, escalation should not be done in subsequent cycles. The dose remains at 200 mg/m^2 per day for the first 5 days of each subsequent cycle except if toxicity occurs. Dose reductions during the maintenance phase should be applied according to Tables 8 and 9. During treatment a complete blood count should be obtained on day 22 (21 days after the first dose of TEMODAL®). The TEMODAL® dose should be reduced or discontinued according to Table 9.

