**Table 9. TEMODAL® Dose Reduction or Discontinuation During Maintenance Treatment**

Toxicity	Reduce TEMODAL® by 1 Dose Levela	Discontinue TEMODAL®
Absolute Neutrophil Count	<1.0 x 10 9 /L	See footnote b
Platelet Count	<50 x 10 9 /L	See footnote b
CTC Non-hematological Toxicity (except for alopecia, nausea, vomiting)	CTC Grade 3	CTC Grade 4b

a: TEMODAL® dose levels are listed in Table 8.

b: TEMODAL® is to be discontinued if dose reduction to <100 mg/m2 is required or if the same Grade 3 non-hematological toxicity (except for alopecia, nausea, vomiting) recurs after dose reduction.

CTC = Common Toxicity Criteria.

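### Temozolomide rules conflict: 10.3 allows a late escalation that Appendix 4 bars, and the Grade 3 stops in 10.1, 4.2 and 6.2 disagree with Table 9

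*Protocol*

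**What the plan says.** **Escalation.** Section 10.3 starts maintenance temozolomide at 150 mg/m² and, if there are no tolerability or toxicity problems, permits 200 mg/m² "po qd in the second or subsequent cycles". The same section opens with "Institutions should follow their standard guidelines for temozolomide". Appendix 4, Maintenance Phase, says: "If the dose was not escalated at Cycle 2, escalation should not be done in subsequent cycles". It also gives criteria for the cycle 2 step: non-haematological toxicity of Grade 2 or less (alopecia, nausea and vomiting excepted), ANC at least 1.5 × 10⁹/L and platelets at least 100 × 10⁹/L. Section 4.2, after describing cycle 1, says "In the next cycle, the temozolomide dose should be escalated", and the synopsis agrees.

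**Stopping.** Section 10.1 says "Temozolomide's 28 days cycle will be repeated 6 times or until grade 3 or higher temozolomide related treatment AE's". It then says "Temozolomide dose may be adjusted or withheld according to the directives in the temozolomide's product monograph (appendix 4"). Section 4.2 and the synopsis also send the reader to Appendix 4 for dose adjustment. Under Table 9, a first Grade 3 non-haematological toxicity (same three exceptions) means a reduction of one dose level. Temozolomide is discontinued at Grade 4, if a dose below 100 mg/m² would be needed, or "if the same Grade 3 non-hematological toxicity (except for alopecia, nausea, vomiting) recurs after dose reduction".

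Two further places contain a Grade 3 stop. In 4.2 and the synopsis the combination runs for six cycles or until a termination event, and that event includes a treatment-emergent AE of Grade 3 or more. Section 6.2 lists Grade 3 or higher toxicity among the reasons for discontinuing study treatment.

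**The concern.** A treating physician can follow one part of the protocol and breach another. For the same patient, one page permits a late increase of a cytotoxic drug and another forbids it; one page stops the drug and another continues it at a lower dose. The first conflict bears directly on patient safety. The second sets how long a patient receives both drugs, because under 4.2 stopping temozolomide for toxicity moves the patient into the Monotherapy Phase.

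There is also a small analysis consequence. Protocol 12.3.3 and SAP 1.3.3 plan an exploratory covariate on how far patients complete the six cycles in light of temozolomide toxicity. If different stop rules are applied to different patients, that covariate mixes the patient's tolerance with the rule that happened to be followed. Cumulative dose can still be computed from doses given.

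**Working it through.** The plan states no figure for this point, so there is none to reproduce. The size of each conflict follows from the dose levels.

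**Inputs.** Five dosing days per 28-day cycle and six cycles (4.2, 10.3); dose levels 100, 150 and 200 mg/m²/day (Appendix 4, Table 8).

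**Dose per cycle** = 5 × daily dose: 500, 750 and 1000 mg/m².

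**Conflict 1: patient not escalated at cycle 2, no later toxicity.** Appendix 4 total = 6 × 750 = 4500 mg/m². If 10.3 is used to escalate at cycle *m*, total = (*m* − 1) × 750 + (7 − *m*) × 1000.

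| Escalated at cycle | Total (mg/m²) | Excess over 4500 |
|---|---|---|
| 3 | 1500 + 4000 = 5500 | 22.2% |
| 4 | 2250 + 3000 = 5250 | 16.7% |
| 5 | 3000 + 2000 = 5000 | 11.1% |
| 6 | 3750 + 1000 = 4750 | 5.6% |

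**Conflict 2: first Grade 3 non-haematological event related to temozolomide, outside the three exceptions.** Assume that the patient was escalated at cycle 2, that the event falls in cycle *k* after that cycle's doses, and that no further toxicity occurs. Total under 10.1 = 750 + (*k* − 1) × 1000. Table 9 reduces to 150 mg/m², so its maximum adds (6 − *k*) × 750.

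| Event in cycle | 10.1 stop (mg/m²) | Table 9 maximum (mg/m²) |
|---|---|---|
| 2 | 1750 | 1750 + 3000 = 4750 |
| 3 | 2750 | 2750 + 2250 = 5000 |
| 4 | 3750 | 3750 + 1500 = 5250 |
| 5 | 4750 | 4750 + 750 = 5500 |
| 6 | 5750 | 5750 |

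For an event in cycle 1 at 150 mg/m², 10.1 gives 750. Table 9 reduces to 100 mg/m² and allows at most 750 + 5 × 500 = 3250.

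For the cycle 2 event, the patient completes 2 of 6 temozolomide cycles under 10.1 and up to 6 of 6 under Table 9. The Table 9 figures are best-case maxima. A patient already at 100 mg/m² would stop under either rule.

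**Which text is the outlier?** On escalation, 4.2, the synopsis and Appendix 4 are compatible, and 10.3 stands alone. On stopping there is no single outlier. Grade 3 stops appear in 10.1, in the termination-event text and in 6.2, while the synopsis, 4.2 and 10.1 itself all refer dose adjustment to Appendix 4. No order of precedence is stated.

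**The case against.** The strongest reply is that the stricter Grade 3 stop appears in several places and may be what the sponsor intends, with Appendix 4 as supporting product information. That stands in part. It means a reviewer should not presume that Table 9 prevails, and that editing 10.1 alone would leave 4.2, the synopsis and 6.2 in conflict with Table 9. It does not remove the need to state which rule governs.

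It can also be said that 10.3 is permissive and conditional, and that temozolomide is background therapy given at one centre. The condition narrows the group who could be escalated late, but Appendix 4 bars that group outright, and 10.3's reference to institutional guidelines adds a third authority.

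A reader might draw stronger conclusions that the documents do not support:

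- *That the 10.1 stop also clashes with Table 9's ANC and platelet reductions.* Section 11.1.1 counts adverse events as "including an abnormal laboratory finding", so the inference is natural. But Table 9 gives counts without grades, and the documents do not reproduce the CTCAE cut-offs needed to say which counts are Grade 3.
- *That stopping temozolomide early costs the patient avelumab doses.* Under 10.1 avelumab continues whether or not the temozolomide cycles are completed, and the note in 9.3.4 says that Grade 3 events due to temozolomide are not a reason to withhold it.
- *That Appendix 4's four-week start should replace the 21-day limit.* The 21-day window is applied consistently in 4.2, inclusion criterion 6 and exclusion criterion 6.
- *That the two-weekly laboratory tests make the day-22 count dispensable.* Appendix 4 pairs that count with Table 9. Tests before each infusion fall at about days 1, 15 and 29, so they do not cover day 22.

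**Conclusion.** The point holds on both conflicts, with different force. The escalation wording in 10.3 is wrong as written: it contradicts Appendix 4 and departs from 4.2 and the synopsis. It would allow 5.6% to 22.2% more temozolomide over six cycles than Appendix 4 in a patient not escalated at cycle 2. The stopping rules are unresolved: for a first Grade 3 non-haematological event in cycle 2, the total is 1750 mg/m² or up to 4750 mg/m² depending on which text is followed. The gap shrinks to nothing for an event in cycle 6.

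These are per-patient figures that assume no further toxicity. The documents give no rate for such events, so the number of the 30 patients affected cannot be stated. A reader might infer that the primary endpoint is compromised. It is not directly, because it counts avelumab-related events; any effect comes only through the length of combined treatment. The sample size and the one-year survival and progression-free thresholds are unaffected.

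**What to change.** 1. **Section 10.3.** Replace the escalation timing with: at cycle 2 only, if the Appendix 4 criteria are met (non-haematological toxicity Grade 2 or less except alopecia, nausea and vomiting; ANC at least 1.5 × 10⁹/L; platelets at least 100 × 10⁹/L). State that institutional guidelines do not override this.
2. **Stopping rule.** The sponsor should choose one rule and write it into 10.1, 4.2, the synopsis and 6.2 together. Either Table 9 governs reduction and discontinuation of temozolomide, or the stricter Grade 3 stop applies and is expressly said to override Table 9.
3. **Leave alone.** Keep the 21-day start window. Do not add wording that excludes the Appendix 4 day-22 blood count.

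The cost is amendment wording in 10.1, 10.3, 4.2, 6.2 and the synopsis. The sample size, decision thresholds and planned analyses do not change. The day-22 count is already in Appendix 4 but falls outside the two-weekly schedule, so a site not now doing it would add one blood count per temozolomide cycle.
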